6.1.2 STANDARD OF CARE STUDY PROCEDURES

The patients will be cleaned with alcohol prior to treatment. After the treatment, a zinc-based sunblock will be applied and if there is any post-treatment pain a cold ice pack will be applied.

The patient will be cleaned with alcohol prior to the skin biopsy and injected with lidocaine to numb the area. Sterile equipment will be used to take a 4mm punch biopsy from the same location on each arm.

6.2 STUDY SCHEDULE

6.2.1 SCREENING

Screening Visit (Day -30 to 0)

- Review subject questionnaire to determine eligibility based on inclusion/exclusion criteria
- Schedule study visits for participants who are eligible and available for the duration of the study
- Provide participants with specific instructions needed to prepare for all their visits

6.2.2 ENROLLMENT/BASELINE

Enrollment/Baseline Visit (Visit 1, Day 0) Treatment #1

- Review in depth the study design with subjects and obtain informed consent of potential participants verified by signature
- Perform examination and verbally review subject's medications, medical history, and subject questionnaire to determine eligibility based on inclusion/exclusion criteria

- Obtain demographic information
- Shave the hair on the subjects' lower arms
- Take digital pictures of subjects' lower arms
- Have evaluator measure the size and number of bruises and skin tears
- Perform the BBL treatment on assigned arm per protocol
- Record adverse events as reported by participant or observed by investigator
- Perform protocol adherence check by study coordinator
- Expected post-procedure side effects and possible emergent situations reviewed with subjects and post-op written instructions given

6.2.3 FOLLOW UP TREATMENTS

2nd Treatment (Visit 2, Day 7 +/- 2 days)

- Record adverse events as reported by participant or observed by investigator.
- Subjects fill out adherence questionnaire and evaluator review to ensure continued eligibility
- Evaluator measures the size and number of bruises and number of skin tears
- Shave bilateral lower arms
- Take digital pictures of subjects' lower arms
- Perform the BBL treatment the second time per protocol
- Record adverse events as reported by participant or observed by investigator.
- Perform protocol adherence check by study coordinator
- Expected post-procedure side and post-op written instructions reviewed

3rd Treatment (Visit 3, Day 14 +/-2 days)

- Record adverse events as reported by participant or observed by investigator.
- Subjects fill out adherence questionnaire and evaluator review to ensure continued eligibility
- Evaluator measures the size and number of bruises and number of skin tears
- Shave bilateral lower arms
- Take digital pictures of subjects' lower arms
- Perform the BBL treatment a third time per protocol
- Record adverse events as reported by participant or observed by investigator
- Perform protocol adherence check by study coordinator
- Expected post-procedure side and post-op written instructions reviewed

4th Treatment (Visit 4, Day 21 +/-2 days)

- Record adverse events as reported by participant or observed by investigator.
- Subjects fill out adherence questionnaire and evaluator review to ensure continued eligibility
- Evaluator measures the size and number of bruises and number of skin tears
- Shave bilateral lower arms
- Take digital pictures of subjects' lower arms
- Perform a BBL treatment on the assigned arm a fourth time per protocol
- Record adverse events as reported by participant or observed by investigator.
- Perform protocol adherence check by study coordinator

Expected post-procedure side and post-op written instructions reviewed

6.2.4 FOLLOW UP VISITS

Follow Up Visit 1 (Visit 5, Day 22 +/-2 days)

- Clean skin with alcohol
- Perform protocol adherence check by study coordinator
- Perform 4mm punch biopsy
- One dissolving suture will be placed in the dermis along with a steri-strip on the top of the skin
- Skin specimens will be bisected, and half will be placed in formalin and half will be placed in RNAlater.
- Skin specimen bottles will be coded and sent for blinded evaluation
- Expected post-procedure side and post-op written instructions reviewed

6.2.5 FINAL STUDY VISIT

Follow-up Visit 2 (Visit 6, Day 51 +/-2 days)

- Record adverse events as reported by participant or observed by investigator.
- Subjects fill out adherence questionnaire and evaluator review to ensure continued eligibility
- Evaluator measures the size and number of bruises and number of skin tears
- Shave bilateral lower arms
- Take digital pictures of subjects' lower arms
- Provide final instructions

6.2.6 EARLY TERMINATION VISIT

- Record adverse events as reported by participant or observed by investigator.
- Collect questionnaires
- Take Digital Photos of subject's lower arms
- Record participant's adherence to treatment program
- Provide final instructions

6.2.7 UNSCHEDULED VISIT

All unscheduled visits will be discouraged unless emergent. All unscheduled visits will be recorded and kept as brief as possible with no active intervention unless a vascular occlusion is suspected, or other emergent health condition is suspected.

6.2.8 SCHEDULE OF EVENTS TABLE

Procedures	Enrollment/Baseline/1st Treatment Visit 1, Day 0	2 nd Treatment Visit Visit 2, Day 7	3 rd Treatment Visit Visit 3, Day 14	4th Treatment Visit Visit 4, Day 21	Follow Up Visit 1 Visit 5, Day 22	Follow Up Visit 2 Visit 6, Day 51
Informed	Х					
consent Demographics	Х					
Medical history	Х					
Subject Questionnaire Study Intervention Evaluation for adverse effects Digital photos	Х	Х	Х	Х		х
Study Intervention	Х	Х	Х	Х		
Evaluation for adverse effects	Х	Х	Х	Х		Х
Digital photos	Х	Х	Х	Х		Х
Evaluator Measurements	Х	Х	Х	Х		х
Skin Biopsy					Х	

6.3 PROHIBITED MEDICATIONS, TREATMENTS, AND PROCEDURES

Changes in any anti-coagulants and prednisone use are prohibited during the study as well as any procedures or surgeries on the treatment arm.

In the event a subject makes changes to their medications or has treatments or procedures, the primary investigator will make the final decision regarding early termination from the study or disregarding certain data from final statistical analysis.

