Subject follow up questionnaires filled out by all subjects

• Study Intervention #4:

Sciton's BBL done a fourth time on the assigned arm according to protocol settings

• Post-Procedure Assessments:

Post-procedure questionnaires filled out by all subjects immediately after treatment

Day 22 +/- 2 Days: Follow-up assessment via skin biopsy

• A 4mm punch biopsy will be done on both the treated and untreated arm approximately 4cm below the crease in the antecubital fossa

Day 51 +/- 2 Days: Follow-up assessment

Follow-up assessments:

Evaluator assessment and measurement

Pictures taken of subject's lower arms

Subjects follow up questionnaires filled out by all subjects

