2.1 BACKGROUND INFORMATION

Senile Purpura is a benign common condition characterized by recurrent formation of ecchymosis on the extensor surfaces of forearms and hands following minor trauma. Other names of this condition are Bateman purpura, named after British dermatologist Thomas Bateman, who first described it in 1818, and actinic purpura, because of its association with sun damage (1).

More recently in 2007, Kaya and Saurat coined the term dermatoporosis to describe the chronic cutaneous fragility of aging skin. Dermatoporosis features include thinning atrophic skin, purpura, skin lacerations and delayed healing (2).

This condition affects over 10% of those aged over 65 years old and is equally common in males and females. Risk factors are known to include the use of oral or topical corticosteroids and anti-coagulants (3).

With age and sun damage, the dermis becomes thin. As a result, this condition results from superficial vessels tearing even with negligible trauma. The subsequent extravasation of blood into the surrounding dermis results in the development of ecchymosis. Histologically, the epidermis is thinned and the dermis demonstrates significantly reduced amounts of collagen replaced by abnormal elastic fibers, as well as extravasated red blood cells (4).

Intense pulsed light (IPL) is non-coherent, non-collimated, polychromatic light energy. IPL emits different wavelengths that target specific chromophores. This makes IPL a versatile therapy with many applications, from the treatment of pigmented or vascular lesions to hair removal and skin rejuvenation. Its large spot size ensures a high skin coverage rate and ease of use over large areas. The treatment has very little downtime given its non-ablative nature which makes it an attractive option. In many cases, IPL is similar to laser therapy in effectiveness, convenience, and safety and together with its versatility will lead to an expanded range of applications and possibilities in the future.

Relevant Clinical Research

Published studies on treatments for senile or actinic purpura or dermatoporosis are very limited. In one small double blinded study (N=14) published in 1995 in The Archives of Dermatology, they showed twice daily treatment with retinoic acid cream resulted in significant reduction in Bateman's actinic purpura after two weeks, however there were no significant differences after that time (6).

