4.2 PARTICIPANT EXCLUSION CRITERIA

An individual who meets any of the following criteria will be excluded from participation in this study:

- Subjects with a history of any arm swelling
- Subjects with allergies to light
- Subjects with auto-immune skin conditions such as lupus, or vitiligo
- Subjects using topical retinol within the last 3 months
- Subjects with any scheduled laser, light, or surgical procedures on the arm during the study
- Subjects unwilling or unable to keep their arms still during digital pictures
- Subjects who are pregnant or nursing
- Subjects with a history of herpes simplex or zoster on their arms
- Subjects with current skin infections, tumors, or dermatitis on the arm
- Subjects with allergies to lidocaine
- Subjects with a history of keloid formation
- Subjects with a history of a bleeding disorder
- Subjects with allergies to adhesives

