4.4 PARTICIPANT WITHDRAWAL ORTERMINATION

4.4.1 REASONS FOR WITHDRAWAL OR TERMINATION

Participants are free to withdraw from participation in the study at any time.

An investigator may terminate participation in the study if:

- The participant's health declines
- The participant needs any surgery or other serious medical interventions
- The participant meets an exclusion criterion (either newly developed or not previously recognized) that precludes further study participation.
- The participant fails to show up for follow-up and final visits

The primary investigator will attempt to visit all participants that have withdrawn or terminated from the trial if they are unable to make their follow-up visits to ensure as much data as possible has been collected and that all safety parameters have been met.

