8 STATISTICAL CONSIDERATIONS

8.1 STATISTICAL HYPOTHESES

Primary Endpoint

$$H_0: \mu_C = 0$$
; $H_1: \mu_C > 0$

- > The null hypothesis is the absolute mean difference in the change from baseline to 30 days after the last treatment on the treatment arm as compared to the non-treatment arm is zero.
- The alternative hypothesis is the absolute mean change from baseline to 30 days after the last treatment on the treatment arm as compared to the non-treatment arm is greater than zero.
 - 1. Let μ_C represent the absolute mean difference between the treated arm as compared to the non-treated arm in the difference in the number of ecchymoses from baseline to 30 days after the last treatment.
 - 2. Let μ_C represent the absolute mean difference between the treated arm as compared to the non-treated arm in the difference in the size of ecchymoses from baseline to 30 days after the last treatment.

A Paired t-test will be used to analyze the primary endpoint. The results of the statistical analysis will be presented as an odds ratio with 95% Confidence intervals. A Shapiro-Wilk Test will be used to assess the normality of data.

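### Section 6.3 bars procedures on the treated arm only, so the two compared arms are not protected alike, and data affected by a procedure are handled by discretion rather than by rule

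*Combined protocol and SAP*

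**What the plan says.** - **Section 6.3, first paragraph**, prohibits "any procedures or surgeries on the treatment arm". The untreated arm is not named.
- **Section 8.1 and the SAP** fix the meaning of the term. The null hypothesis is about change "on the treatment arm as compared to the non-treatment arm is zero", so the treatment arm is the BBL-treated limb.
- **Section 3.2.2** makes the primary endpoint the treated versus untreated difference in change in area and number of ecchymoses, from baseline to the Day 51 visit. Section 8.1 analyses it by paired t-test.
- **Section 4.2** excludes "Subjects with any scheduled laser, light, or surgical procedures on the arm during the study". It does not say which arm.
- **Section 4.4.1** lists two grounds on which an investigator may end participation: "The participant needs any surgery or other serious medical interventions", and "The participant meets an exclusion criterion (either newly developed or not previously recognized) that precludes further study participation". Both are discretionary, and neither is limited to one arm.
- **Section 6.3, second paragraph**, says that if a subject "has treatments or procedures, the primary investigator will make the final decision regarding early termination from the study or disregarding certain data". No arm is named and no criteria are given.
- **Schematic of Study Design, Day 22**: "A 4mm punch biopsy will be done on both the treated and untreated arm". The protocol's own invasive procedure is therefore balanced.

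**The concern.** In a split-arm design the untreated limb carries the same weight in the estimate as the treated one. A restriction that attaches to treatment and not to side is not balanced by randomising left or right, because the protected limb is always the BBL limb.

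The population makes this relevant. Section 2.1 describes the condition as "recurrent formation of ecchymosis on the extensor surfaces of forearms and hands following minor trauma", so a small procedure could leave a countable lesion. The same section names anti-coagulants as a risk factor, and Section 6.3 bars only changes in their use. The group is small and the Précis lets a subject enter with one lesion per arm, so single lesions matter.

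At stake is whether a difference at Day 51 reflects BBL alone, or partly a difference in what the two arms were allowed to undergo.

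**Working it through.** The plan has no figure to reproduce: Section 8.4 gives no sample-size calculation, and no SD, effect size or alpha is stated. The check has three steps.

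**1. What is left uncovered on the untreated arm?** I read Section 6.3 as meaning non-study procedures.

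| Event on the untreated arm | Text that reaches it | Effect of that text |
|---|---|---|
| Laser, light or surgical procedure planned at entry | 4.2 | Excluded |
| Such a procedure arising later | 4.4.1, 6.3 second paragraph | Discretionary |
| Any surgery | 4.4.1, 6.3 second paragraph | Discretionary |
| Minor non-surgical procedure (venepuncture is my example; the documents do not mention it) | 6.3 second paragraph only | Permitted; data kept or dropped by discretion |

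On the treated arm, all four are prohibited outright by the first paragraph of Section 6.3.

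Section 8.5 keeps the evaluator separate from the primary investigator and limits knowledge of the assignment to the treating investigator and the coordinator. Nothing requires whoever decides to drop data under Section 6.3 to be masked. The schedule in Section 6.2.8 has no row for procedures. The questionnaires are not reproduced, so they may or may not ask.

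**2. Which way does a bruise act?** For subject i, let D_i = (untreated change) − (treated change), with change = Day 51 − Day 0. Positive values favour BBL. Suppose a procedure adds k lesions to the untreated arm.

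| Lesions present at | Shift in D_i |
|---|---|
| Day 51 only | +k (towards BBL) |
| Neither Day 0 nor Day 51 | 0 |
| Both days | 0 |
| Day 0 only | −k (against BBL) |

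A laser or light procedure that cleared lesions on the untreated arm would also act against BBL.

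**3. How large could it be?** The Précis gives 5 subjects with purpura and restricts the primary endpoints to them, so n = 5. If one subject is affected, the mean shifts by k/n:

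- k = 1: 1/5 = 0.2 lesions.
- k = 2, or two subjects with one lesion each: 2/5 = 0.4 lesions.
- If all 10 subjects were analysed, the shift for one lesion would be 1/10 = 0.1.
- For area, a bruise of A cm² shifts the mean by A/5 cm².

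If each subject independently has probability p of such a bruise at Day 51, the expected shift is p × k. A simulation of the paired t-test used 100,000 runs with n = 5, normal differences and no true effect. It took a one-sided 5% level, which is assumed because none is stated, SD of the differences 1, 2 or 4 lesions, and k = 1 or 2. All values of p, k and SD are assumptions.

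| p | Expected shift, p × k | False-positive rate |
|---|---|---|
| 0 | 0 | about 5% |
| 0.1 | 0.1 to 0.2 | about 5 to 8% |
| 0.2 | 0.2 to 0.4 | about 6 to 12% |
| 0.4 | 0.4 to 0.8 | about 7 to 25% |

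The low ends come from SD 4 with k = 1, and the high ends from SD 1 with k = 2.

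**The case against.** The strongest reply is that the untreated arm is already covered. Section 4.2 is arm-neutral, Section 4.4.1 allows termination for surgery at any site and for an exclusion criterion met later, and the second paragraph of Section 6.3 applies to procedures on either arm. The study biopsy is taken from both. This narrows the point to minor or unscheduled non-surgical procedures but does not close it. Discretion without criteria or a masking requirement is a weaker safeguard than the outright prohibition on the other limb.

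A reader might infer that subjects' procedures are steered to the untreated arm. The documents do not support that: they fail to prohibit such procedures there, which is not the same as directing them there, and nothing shows that any occurred. A reader might also infer that the error must always favour BBL. Step 2 of the working shows that it need not: the direction holds only for new lesions still present at Day 51.

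It is also fair to say that 0.2 is simply 1/n, and would follow from any single miscounted lesion. It shows sensitivity, not likely size. Finally, leaving out lesions at a procedure site is a new endpoint rule, and attributing a bruise to a procedure takes judgement in a condition where trivial trauma produces lesions. That stands, and is why the fix includes an analysis of all lesions.

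**Conclusion.** The point holds as an asymmetry in the written rules, with a potential bias of unknown size. Section 6.3 restricts procedures on one of the two compared limbs, Section 4.2 does not make that distinction, and the remaining text covers the gap only by discretion that need not be masked. Confidence in the asymmetry is high.

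Confidence in the amount of bias is low. A shift towards BBL requires that such a procedure takes place on the untreated arm, that it leaves a lesion still visible at Day 51, and that the data are kept. The documents give no frequency for any of these. The 0.2 and 0.4 lesions, and the simulated error rates, are illustrations on assumed inputs and do not estimate what this trial would see. The correction is worth making because it costs little and the group is small enough for one lesion to register.

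**What to change.** 1. **Reconcile Sections 6.3 and 4.2** so that the same wording on non-study procedures covers both arms. Which procedures it should restrict is for the investigator to settle; the statistical requirement is only that the arms are treated alike. Cost: one phrase.
2. **Record the arm, site and date** of any procedure that does occur, at every visit up to Day 51. Cost: one questionnaire line.
3. **Replace the discretion in the second paragraph of Section 6.3, as it bears on data,** with a rule written before the data are seen. It should state how lesions at a documented procedure site enter the count and area, apply alike to both arms (study biopsy sites included), and be carried out by the masked evaluator. Cost: one analysis rule, and some judgement in attributing lesions.
4. **Report an analysis of all lesions** as a sensitivity check, so that a reader can see whether the attribution matters. Cost: one further paired analysis of each primary measure.

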2.3 POTENTIAL RISKS AND BENEFITS

2.3.1 KNOWN POTENTIAL RISKS

Common potential risks of BBL include swelling, pain, scabbing, blistering, reduction of hair and lentigenes, erythema, pruritus, lightening and darkening of the skin, and reactivation of herpes infection. Rare but potential risks of BBL include severe burn, skin ulceration, scarring and infection.

Common potential risks of a skin biopsy include bleeding and scarring while rare but potential risks include infection and allergy to the lidocaine, bandages, or sutures used in the procedure.

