6.5 RESCUE MEDICATIONS, TREATMENTS, AND PROCEDURES

If patients develop an infection during the trial, they will be prescribed the appropriate anti-viral or anti-bacterial medication but will continue in the study.

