8.5 MEASURES TO MINIMIZE BIAS

ENROLLMENT/ RANDOMIZATION/ MASKING PROCEDURES

In order to avoid bias, the subjects will be randomized to receive treatment on either their left or right arm. All evaluators of pictures will be blinded as to which technique was used on which side. In order to avoid bias, the evaluator will not be the primary investigator.

To ensure only the clinical investigator performing the procedures and the study coordinator know

the assignment of arms, each subject will have an envelope assigned to them to be held by the study coordinator with the subject's name on the outside and the assignment on the inside. Only during treatments does the study coordinator allow the clinical investigator to see the inside of the envelope.

The skin biopsy samples will be coded to ensure blinded analysis.

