10.3 PROTOCOL DEVIATIONS

A protocol deviation is any noncompliance with the clinical trial protocol. The noncompliance may be either on the part of the participant, the investigator, or the study site staff. As a result of deviations, corrective actions are to be developed by the site and implemented promptly. It is the responsibility of the site to use continuous vigilance to identify and report deviations within 7 working days of identification of the protocol deviation, or within 7 working days of the scheduled protocol-required activity. All deviations must be addressed in study source documents, reported to the IRB and sponsor. The site PI/study staff is responsible for knowing and adhering to their IRB requirements.

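### Section 6.3 lets the primary investigator leave collected data out of the final analysis without a stated criterion, unit, deadline or blinding, and no analysis set limits this

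*Combined protocol and SAP*

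**What the plan says.** Section 6.3 opens with a short list of prohibitions: "Changes in any anti-coagulants and prednisone use are prohibited during the study", together with procedures or surgeries on the treatment arm. The next sentence is triggered as follows: "In the event a subject makes changes to their medications or has treatments or procedures". In that event, "the primary investigator will make the final decision regarding early termination from the study or disregarding certain data from final statistical analysis". Nothing further is said about which data, on what grounds, or when.

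On the analysis, section 8.1 and the SAP carry the same text: "A Paired t-test will be used to analyze the primary endpoint", with a 95% confidence interval and a Shapiro-Wilk test. Neither they nor the rest of section 8 name an analysis set, a missing-data rule or a sensitivity analysis. Section 8.4 gives no sample-size calculation, because the study is a pilot.

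On masking, section 8.5 blinds the evaluators of pictures and codes the biopsy samples. Its envelope procedure has this aim: "To ensure only the clinical investigator performing the procedures and the study coordinator know" the assignment. The decision to leave data out is not mentioned.

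**The concern.** This is more than a gap. The plan contains a rule on exclusion, and the rule is one person's discretion over data already collected. If the decision is taken with knowledge of arm and result, it can move the estimate in either direction, and in a set of five or ten pairs a single exclusion carries real weight.

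The split-arm design gives partial protection. A change in an anti-coagulant or prednisone acts on both arms of the same subject, so the paired difference is less affected. The design does not protect against selective removal of pairs, visits or measures. Nor does it protect against a treated-arm reaction that itself leads to medication. Section 2.3.1 states: "Rare but potential risks of BBL include severe burn, skin ulceration, scarring and infection". If such a subject were removed because of the resulting prescription, the exclusion could be related to the treated arm's outcome, and deciding blind would not cure that.

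**Working it through.** **1. Does another section supply the missing rule?**

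| Section | What it governs | Does it settle data exclusion? |
|---|---|---|
| 4.4.1 | Reasons for ending participation; an attempt to visit those who left | No: participation, not analysis |
| 6.5 | Subjects treated for infection: "they will be prescribed the appropriate anti-viral or anti-bacterial medication but will continue in the study" | No: they stay in the study, but use of their data is not stated |
| 8.5 | Masking of picture evaluators and biopsy samples | No: the exclusion decision is not covered |
| 10.3 | Sites must "identify and report deviations within 7 working days of identification of the protocol deviation" | No: a deadline for reporting, not for excluding |
| 8.1 and SAP | Hypotheses, paired t-test, interval, normality test | No: no analysis set |

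**2. How much data is one pair?** The primary endpoints in the synopsis are confined to those with senile purpura. The Précis describes five older subjects with lesions on each arm and five subjects under 35. That gives 1/5 = 20% per pair. Section 4.1, however, requires an ecchymosis greater than 1 cm on each arm of every participant. If that applies to all ten, the share is 1/10 = 10%.

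**3. Cost in precision of losing one pair, for any reason.** The 95% half-width in SDs of the paired differences is t(0.975, n−1)/√n.
- n = 5: 2.776/√5 = 1.24. n = 4: 3.182/√4 = 1.59.
- n = 10: 2.262/√10 = 0.72. n = 9: 2.306/√9 = 0.77.

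This shows how much one pair weighs. It does not measure the effect of discretion.

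**4. Illustration of informed discretion.** The plan gives no alpha, power, effect or SD, so there is no figure of its own to reproduce. Assumptions: one-sided 5%, one endpoint, independent normal paired differences, no true effect, at most one pair dropped, and a decider who knows the result and always keeps whichever analysis rejects.

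Test: T = mean/(s/√n), rejecting when T > t(0.95, n−1). The critical values are 2.132 (n = 5) and 2.353 (n = 4), or 1.833 (n = 10) and 1.860 (n = 9). The overall rate is the probability that the full analysis or an allowed reduced analysis rejects. Simulation, 400,000 runs:

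| Case | n = 5 | n = 10 |
|---|---|---|
| No exclusion | 5.0% | 5.0% |
| One pair dropped regardless of outcome | 5.0% | 5.0% |
| One eligible pair, informed choice | 7.1% | 6.4% |
| Any one pair may be dropped, informed choice | 15.4% | 15.1% |

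As a check, with one eligible pair the rate must lie between 5% and 5% + 5% = 10%, and it does. Two-sided at 5%, the one-eligible-pair figures are 7.4% and 6.6%.

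**The case against.** Several objections have force.

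- **Scope of the trigger.** The sentence follows directly on the prohibited list, under a heading about prohibited items, so it may be meant for those items only. The wording also permits any medication change, treatment or procedure. Both readings are open. Whether a prescription under section 6.5 would trigger 6.3 depends on the wider one. Neither reading supplies a criterion for dropping data.
- **Split-arm protection.** The named drugs are systemic and act on both arms, which weakens any link between trigger and paired difference. This stands for those drugs, but it does not answer selective removal.
- **Size.** The documents give no trigger rate and no correlation between trigger and outcome, and section 2.3.1 calls infection rare. Any range built on assumed values for these would have no source, so none is claimed.
- **Number of pairs.** Five is not settled, because section 4.1 points to ten. Both are therefore shown.
- **Feasibility of blinding.** Section 6.3 prohibits procedures on the treatment arm, and whether one has occurred cannot be judged without knowing which arm that is. A demand for full blinding would not work, and the fix allows for this.

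A reader might infer that the primary investigator is the unmasked treating investigator. The documents do not say so. Section 8.5 says only that the evaluator is not the primary investigator and that the person performing the procedures knows the assignment. What can be said is that nothing requires the decision to be made blind.

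**Conclusion.** The point holds as a matter of text: collected data may be left out at one person's discretion, with no criterion, unit, deadline or blinding, and no analysis set limits it. One whole pair is 20% of the primary data with five pairs, or 10% with ten.

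The false-positive figures are illustrations that rest on the assumptions listed in the working. With one eligible pair, 5% becomes about 7.1% (n = 5) or 6.4% (n = 10). It would be wrong to read the figure of about 15% as the trial's expected error rate. It needs every pair to be open to exclusion and a decider who always exploits that, so it is an upper bound. The documents give no sign that the discretion would be misused. Because this is a pilot, the main risk is to the estimate and its interval rather than to a formal error rate. The change is worth making because it is cheap.

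**What to change.** In section 6.3, delete the option to leave data out of the final analysis. The investigator's decision on early termination is a clinical matter and is not touched here.

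In section 8.1 and the SAP, add wording such as:

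> All randomised subjects with senile purpura who have baseline and Day 51 measurements on both arms enter the primary analysis, whatever their medication changes, treatments or procedures, including subjects whose participation was ended but who were measured. Any exclusion is a sensitivity analysis only, reported beside the primary result. Its reasons and the data affected are listed in advance. It is decided by someone without access to the outcome data, who is also blind to the assigned arm unless the reason is a procedure on one arm.

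**Cost.** Wording only; no extra visit or procedure. The downside is that some subjects with deviations stay in the primary analysis, possibly including one with a procedure on a single arm. The sensitivity analysis shows their influence.

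**Limits.** Subjects whose participation ends and who are not measured at Day 51 are still missing. Section 4.4.1 provides for an attempt to visit them, but the early termination visit in section 6.2.6 lists photographs and no lesion count or area. The proposed set also depends on who counts as having senile purpura, so the Précis and section 4.1 need to be reconciled.
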